#### 9.5.4.2 Reporting of Pregnancy and Exposure to Study Drug Through Breastfeeding

Any pregnancy in which either the estimated date of conception is before the last visit or within 28 days of last study treatment, or any exposure to study drug through breastfeeding during study treatment or within 28 days of last study treatment, must be reported.

If an adverse outcome of a pregnancy is suspected to be related to study drug exposure, this should be reported regardless of the length of time that has passed since the exposure to study treatment.

A congenital anomaly, death during perinatal period, an induced abortion, or a spontaneous abortion are considered to be an SAE and should be reported in the same time frame and in the same format as all other SAEs (see Reporting of Serious Adverse Events [Section 9.5.4.1]).

Pregnancies or exposure to study drug through breastfeeding must be reported by fax or email as soon as possible but no later than 1 business day from the date the investigator becomes aware of the pregnancy. The contact information for the reporting of pregnancies and exposure to study drug through breastfeeding is provided in the Investigator Study File. The Pregnancy Report Form must be used for reporting. All pregnancies must be followed to outcome. The outcome of the pregnancy must be reported as soon as possible but no later than 1 business day from the date the investigator becomes aware of the outcome.

A subject who becomes pregnant must be withdrawn from the study.

#### 9.5.4.3 Reporting of Events Associated with Special Situations

##### 9.5.4.3.1 REPORTING OF ADVERSE EVENTS ASSOCIATED WITH STUDY DRUG OVERDOSE, MISUSE, ABUSE, OR MEDICATION ERROR

Adverse events associated with study drug overdose, misuse, abuse, and medication error refer to AEs associated with uses of the study drug outside of that specified by the protocol. Overdose, misuse, abuse, and medication error are defined as follows:

Overdose	Accidental or intentional use of the study drug in an amount higher than the protocol-defined dose.
Misuse	Intentional and inappropriate use of study drug not in accordance with the protocol.
Abuse	Sporadic or persistent intentional excessive use of study drug accompanied by harmful physical or psychological effects.

**Medication error** Any unintentional event that causes or leads to inappropriate study drug use or subject harm while the study drug is in the control of site personnel or the subject.

All AEs associated with overdose, misuse, abuse, or medication error should be captured on the Adverse Event CRF and also reported using the procedures detailed in Reporting of Serious Adverse Events ([Section 9.5.4.1](#)) even if the AEs do not meet serious criteria. Abuse is always to be captured as an AE. If the AE associated with an overdose, misuse, abuse, or medication error does not meet serious criteria, it must still be reported using the SAE form and in an expedited manner but should be noted as nonserious on the SAE form and the Adverse Event CRF.

#### 9.5.4.3.2 REPORTING OF STUDY-SPECIFIC EVENTS

Study-specific events, consisting of clinically significant bleeding, should always be considered as serious important medical events and be entered on the Adverse Event CRF and reported using the procedures detailed in Reporting of Serious Adverse Events ([Section 9.5.4.1](#)), even if the study-specific event does not meet other serious criteria.

#### 9.5.4.4 Expedited Reporting

The sponsor must inform investigators and regulatory authorities of reportable events, in compliance with applicable regulatory requirements, on an expedited basis (ie, within specific time frames). For this reason, it is imperative that sites provide complete SAE information in the manner described above.

#### 9.5.4.5 Breaking the Blind

Not applicable.

#### 9.5.4.6 Regulatory Reporting of Adverse Events

Adverse events will be reported by the sponsor or a third party acting on behalf of the sponsor to regulatory authorities in compliance with local and regional law and established guidance. The format of these reports will be dictated by the local and regional requirements.

#### 9.5.5 Completion/Discontinuation of Subjects

A subject may elect to discontinue the study at any time for any reason. All subjects who discontinue the study are to complete the study's early discontinuation procedures indicated in the Schedule of Procedures/Assessments (Table 5).

The investigator will promptly explain to the subject involved that the study will be discontinued for that subject and provide appropriate medical treatment and other necessary measures for the subject. A subject who has ceased to return for visits will be followed up by mail, phone, or other means to gather information such as the reason for failure to return, the

status of treatment compliance, the presence or absence of AEs, and clinical courses of signs and symptoms.

Subjects who discontinue early from the study will be discontinued for 1 of these reasons: AE(s), lost to follow-up, subject choice, (ie, subject chooses to discontinue from the treatment but is willing to participate in the Follow-Up portion of the study), progression of disease, withdrawal of consent (ie, subject no longer wishes to participate in the study and be contacted), pregnancy, sponsor discontinuation of the study, or other. Study disposition information will be collected on the Subject Disposition From Treatment Phase CRF page.

#### **9.5.6 Abuse or Diversion of Study Drug**

Not applicable.

#### **9.5.7 Confirmation of Medical Care by Another Physician**

The investigator will instruct subjects to inform site personnel when they are planning to receive medical care by another physician. At each visit, the investigator will ask the subject whether he/she has received medical care by another physician since the last visit or is planning to do so in the future. When the subject is going to receive medical care by another physician, the investigator, with the consent of the subject, will inform the other physician that the subject is participating in the clinical study.

### **9.6 Data Quality Assurance**

This study will be organized, performed, and reported in compliance with the protocol, SOPs, working practice documents, and applicable regulations and guidelines. Site audits will be made periodically by the sponsor's or the CRO's qualified compliance auditing team, which is an independent function from the study team responsible for conduct of the study.

#### **9.6.1 Data Collection**

Data required by the protocol will be collected on the CRFs and entered into a validated data management system that is compliant with all regulatory requirements. As defined by ICH guidelines, the CRF is a printed, optical, or electronic document designed to record all of the protocol-required information to be reported to the sponsor on each study subject.

Data collection on the CRF must follow the instructions described in the CRF Completion Guidelines. The investigator has ultimate responsibility for the collection and reporting of all clinical data entered on the CRF. The investigator or designee as identified on Form FDA 1572 must sign the completed CRF to attest to its accuracy, authenticity, and completeness.

Completed, original CRFs are the sole property of Eisai and should not be made available in any form to third parties without written permission from Eisai, except for authorized representatives of Eisai or appropriate regulatory authorities.

## 9.6.2 Clinical Data Management

All software applications used in the collection of data will be properly validated following standard computer system validation that is compliant with all regulatory requirements. All data, both CRF and external data (eg, laboratory data), will be entered into a clinical system.

## 9.7 Statistical Methods

All statistical analyses will be performed by the sponsor or designee after the study is completed and the database is locked and released and a snapshot of the database is obtained and released. Statistical analyses will be performed using SAS software or other validated statistical software as required. Details of the statistical analyses will be included in a separate statistical analysis plan (SAP).

### 9.7.1 Statistical and Analytical Plans

The statistical analyses of study data are described in this section. Further details of the analytical plan will be provided in the SAP, which will be finalized before database lock.

#### 9.7.1.1 Study Endpoints

##### 9.7.1.1.1 PRIMARY ENDPOINT

The primary efficacy endpoint is ORR based on investigator assessment, defined as the proportion of subjects who have a BOR of CR or PR.

##### 9.7.1.1.2 SECONDARY ENDPOINTS

The secondary efficacy endpoints are:

- PFS based on investigator assessment – defined as the time from date of first dose of study drug to date of first documentation of disease progression or death, whichever occurs first.
- OS – defined as the time from the date of first dose of study drug until date of death from any cause.

##### 9.7.1.1.3 EXPLORATORY ENDPOINTS

The exploratory endpoints are:

- ORR based on IIR assessment.
- PFS based on IIR assessment.
- CBR is the proportion of subjects who have a BOR of CR or PR or durable SD. Stable disease must be achieved at  $\geq 23$  weeks after first lenvatinib administration to

be considered durable SD. The CBR will be determined based on both investigator and IIR assessments.

- DCR is the proportion of subjects who have a BOR of CR, PR, or SD. The DCR will be determined based on both investigator and IIR assessments.
- DOR is defined as the time from the date that the criteria are met for CR or PR (whichever is recorded first) to the date that PD is objectively documented or death, whichever occurs first. The DOR will be determined based on both investigator and IIR assessments.

#### 9.7.1.2 Definitions of Analysis Sets

The Full Analysis Set (FAS) includes subjects who received at least 1 dose of the study drugs. This will be the analysis set for all efficacy and safety evaluations.

The Evaluable Analysis Set (EAS, a subset of the Full Analysis Set) includes all subjects who have both an evaluable baseline tumor assessment and an evaluable postbaseline tumor assessment, unless the subjects are discontinued because of disease progression or toxicity. This will be used for the sensitivity analyses of efficacy.

The PK Analysis Set will include all subjects who received at least one dose of study drug and have evaluable lenvatinib plasma and/or everolimus whole blood concentration data.

The Pharmacodynamic Analysis Set will include all subjects who received at least one dose of study drug and have evaluable pharmacodynamics data.

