### **Analysis Sets**

The Full Analysis Set (FAS) includes subjects who received at least 1 dose of the study drugs. This will be the analysis set for all efficacy and safety evaluations.

The Evaluable Analysis Set (EAS, a subset of the FAS) includes all subjects who have both an evaluable baseline tumor assessment and an evaluable postbaseline tumor assessment, unless the subjects are discontinued because of disease progression or toxicity. This will be used for the sensitivity analyses of efficacy.

The Pharmacokinetic Analysis Set will include all subjects who received at least one dose of study drug and have evaluable lenvatinib plasma and/or everolimus whole blood concentration data.

The Pharmacodynamic Analysis Set will include all subjects who received at least one dose of study drug and have evaluable pharmacodynamics data.

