### 9.3.3 Removal of Subjects From Therapy or Assessment

The investigator may discontinue treating a subject with study treatment or withdraw the subject from the study at any time for safety or administrative reasons. The subject may decide to discontinue study treatment or withdraw from the study at any time for any reason.

The reason for discontinuation will be documented. If a subject discontinues study treatment, the subject will enter the Follow-Up Period and complete protocol-specified off-treatment visits, procedures, and survival follow-up unless the subject withdraws consent. The investigator should confirm whether a subject will withdraw from study treatment but agree to continue protocol-specified, off-treatment study visits, procedures, and survival follow-up, or whether the subject will withdraw consent. If a subject withdraws consent, the date will be documented in the source documents. The Subject Discontinuation From Treatment Phase CRF page will be completed indicating the reason for discontinuation. In addition, the date of last dose of study drug(s) will be recorded on the Study Drug Dosing CRF page.

During the Follow-Up Period, subjects who have discontinued study treatment before disease progression will continue to undergo tumor assessment every 8 weeks  $\pm$ 1 week until disease progression is documented or another anticancer therapy is initiated.

All subjects will be followed for survival until death, except where a subject withdraws consent or the sponsor chooses to halt survival follow-up after completion of the primary study analysis. Subjects will be followed for survival every 12 weeks  $\pm$ 1 week after the End of Treatment Visit. If a clinic visit is not feasible, follow-up information may be obtained via telephone or email.

A subject who discontinues study treatment should be followed for subsequent protocol-specified visits and procedures. If a subject discontinues study drug(s) but remains in the study, the set of End of Treatment procedures will be administered, and protocol-specified information will be collected. The reason for discontinuation from study drug(s) should be collected on the Subject Disposition From Treatment Phase CRF page. In addition, the date of last dose of study drug(s) will be recorded on the Study Drug Dosing CRF page. If a subject discontinues study treatment and the study at the same time, the end-of-study procedures (Final Visit) will be followed (see [Section 9.5.5](#)).

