#### 9.7.1.6 Efficacy Analyses

##### 9.7.1.6.1 PRIMARY EFFICACY ANALYSIS

Primary endpoint ORR assessed by investigator review will be analyzed using the Full Analysis Set. Subjects who did not have a tumor assessment for any reason will be considered as nonresponders and included in the denominator when calculating response rate.

In this population, ORR in the historical control is assumed to be 8% ([Hudes et al., 2007](#)). The ORR in this study is estimated as 25%, which is deemed a clinical meaningful improvement. Hence, the null and alternative hypotheses are set as follows:

$$H_0: \text{ORR} = 8\%$$

$$H_a: \text{ORR} \geq 25\%$$

Simon's Two-Stage Design ([Simon, 1989](#)) is used in hypothesis testing for the primary endpoints. The interim futility analysis after Stage 1 allows for an early evaluation of efficacy results in order to stop the study early in the case of low anticancer activity. A minimum of 2 responders as assessed by ORR in the Stage 1 subjects ( $n_1=16$ ) is required in the interim analysis for the study to proceed to Stage 2, in which 15 more subjects may be enrolled. In the final analysis of ORR, a minimum of 6 responders is required in Stages 1 and 2 subjects combined ( $n=31$ ) to claim the superiority of study treatment over historical controls.

The ORR based on investigator assessment in the final analysis will be calculated and a 2-sided Clopper–Pearson 95% confidence interval (CI) will be constructed.

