#### 9.7.1.6.4 FORMAL ANALYSES OF ORR, PFS, AND OS

A formal analysis will be carried out after all subjects have been enrolled and on study treatment for at least 6 months or have discontinued due to disease progression, death, or toxicity. Since the primary endpoint ORR data are expected to be observed sooner than the secondary endpoints, the timing of the formal analysis is chosen such that the secondary endpoints, PFS and OS, will be adequately described. The primary population for efficacy and safety analyses is the FAS.

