#### 9.7.1.6.5 SENSITIVITY ANALYSES

The above efficacy analyses will be conducted in the EAS as sensitivity analyses.

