### 9.7.3 Interim Analysis

An interim analysis may be performed by the sponsor after 16 subjects in Stage 1 have completed at least 2 tumor assessments (eg, Week 16 tumor assessments), unless discontinued due to disease progression, death or toxicity. If one or no responders are observed in the interim analysis, the study will be stopped early for futility and subjects on study at that time will continue treatment under the discretion of the investigator. If two or more responders are confirmed before the planned interim analysis and the safety profiles of both drugs are acceptable, the study will continue to Stage 2 and a formal interim analysis may be waived. There will be no enrollment gap for the interim analysis.

At interim analysis, the probabilities of early futility stopping are 0.6299 under  $H_0$ : ORR=8% and 0.0635 under  $H_a$ : ORR $\geq 25\%$ , respectively.

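### The Evaluable Analysis Set does not excuse a missing scan because of death, yet it is used for every efficacy analysis including PFS and OS, so some early deaths can drop out of them

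*Protocol*

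**What the plan says.** The protocol defines the EAS twice in the same terms, in the synopsis (Analysis Sets) and in Section 9.7.1.2. It is a subset of the FAS and "includes all subjects who have both an evaluable baseline tumor assessment and an evaluable postbaseline tumor assessment, unless the subjects are discontinued" for one of two reasons. Section 9.7.1.2 names them and gives the purpose of the set: "unless the subjects are discontinued because of disease progression or toxicity. This will be used for the sensitivity analyses of efficacy".

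Section 9.7.1.6.5 sets the scope: "The above efficacy analyses will be conducted in the EAS as sensitivity analyses". The analyses above that sentence are ORR (9.7.1.6.1), PFS and OS (9.7.1.6.2), the exploratory endpoints (9.7.1.6.3) and the formal analysis (9.7.1.6.4).

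Two other rules use a similar list and do name death. The formal analysis waits until subjects have enough time on treatment "or have discontinued due to disease progression, death, or toxicity" (9.7.1.6.4). The interim analysis waits for two tumor assessments "unless discontinued due to disease progression, death or toxicity" (9.7.3).

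For the primary ORR analysis in the FAS, 9.7.1.6.1 says: "Subjects who did not have a tumor assessment for any reason will be considered as nonresponders and included in the denominator".

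**The concern.** Death is part of the PFS event and is the whole of the OS event (9.7.1.1.2), and both times run from first dose. Membership of the EAS, however, depends on a scan due about eight weeks later. A subject who dies before that scan, and was not recorded as discontinued for progression or toxicity, is removed together with the event.

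The FAS treats the same subject as a nonresponder in the denominator and as an event for PFS and OS. A sensitivity analysis ought to test that result; this one can remove some of the worst outcomes from it.

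Two further features make membership uncertain:

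- **Recording of reasons.** The discontinuation reasons in 9.5.5 include adverse events, progression and a residual category, but not death. A sudden death, an unrelated death, or a death after stopping by choice has no clear route into the exception.
- **Wording of the exception.** A sentence that includes everyone with both scans, followed by an unless-clause, does not say whether subjects who stopped for progression or toxicity are kept or removed. Keeping them is probably what is meant.

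The filter also removes living subjects. Section 9.5.5 allows for the case where the "subject chooses to discontinue from the treatment but is willing to participate in the Follow-Up portion of the study", and 9.3.3 says "All subjects will be followed for survival until death, except where a subject withdraws consent". Such a subject without an evaluable scan has a known survival outcome, which the EAS analysis of OS discards.

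**Working it through.** **The plan's own figures.** An exact two-stage binomial calculation (continue with at least 2 of 16, reject with at least 6 of 31) gives a type I error of 0.0319 at an ORR of 8% and power of 0.8053 at 25%. Both match Section 9.7.2. They rest on the FAS and do not depend on the EAS definition.

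**Who is excused a missing postbaseline scan, or a minimum follow-up**

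| Rule | Progression | Toxicity | Death |
|---|---|---|---|
| EAS membership (synopsis, 9.7.1.2) | yes | yes | not named |
| Formal analysis timing (9.7.1.6.4) | yes | yes | yes |
| Interim analysis timing (9.7.3) | yes | yes | yes |

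Elsewhere the protocol lists death beside the other two reasons, so it cannot safely be assumed to lie within them in the EAS definition.

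**How many subjects could be affected.** The protocol gives no figure. As an illustration, take an exponential survival curve with the historical median OS of 11.6 months from Section 7.1, and the first scan at Week 8 (9.5.1.2.1).

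- Week 8 in months: 56/30.44 = 1.84
- Probability of death before Week 8: 1 − exp(−ln 2 × 1.84/11.6) = 0.104
- Expected deaths among 31 subjects: 31 × 0.104 = 3.2

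This counts deaths from any cause. Deaths recorded as discontinuation for progression or toxicity stay in the set on the likely reading. I therefore take d, the number dropped, as 0 to 3, with 3 as an upper bound.

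**Effect on ORR.** With 6 responders, the EAS rate is 6/(31 − d).

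**Effect on PFS and OS.** If d early deaths are removed and nobody is censored before the last of them, later Kaplan–Meier estimates satisfy S_EAS(t) = S_FAS(t) × 31/(31 − d). On the same exponential curve, S_FAS(12 months) = exp(−ln 2 × 12/11.6) = 0.488.

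| d | ORR with 6 responders | Factor 31/(31 − d) | 12-month OS |
|---|---|---|---|
| 0 | 6/31 = 19.4% | 1 | 48.8% |
| 1 | 6/30 = 20.0% | 1.033 | 50.4% |
| 2 | 6/29 = 20.7% | 1.069 | 52.2% |
| 3 | 6/28 = 21.4% | 1.107 | 54.0% |

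Each dropped death adds about 0.6 to 0.7 percentage points to ORR. The relative rise in later PFS and OS estimates is 3.3%, 6.9% or 10.7%.

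**The opposite effect on OS.** Dropping one living subject without a scan who survives past 12 months gives (31 × 0.488 − 1)/30 = 47.1%, down from 48.8%.

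**The case against.** The strongest reply is that no conclusion of the trial rests on the EAS. The FAS is the primary population for efficacy and safety, the success rule uses it, and PFS and OS are described without a hypothesis test. Any EAS figure will appear against a FAS figure that keeps every treated subject, so a shift would be visible. This stands, and it is why the point is minor.

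Second, the gap is narrow. A fatal drug-related event can be read as toxicity and a death from the cancer as progression. What remains is mainly unrelated death, or death after stopping by choice. The count may be zero. Three dropped deaths would require nearly all of the roughly 3.2 expected early deaths to fall outside both reasons, in a population limited to ECOG 0 to 1 without CNS metastases. This also stands: the values for 2 and 3 are bounds, not expectations.

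Third, the timing rules serve a different purpose from a population definition, so the differing lists are not a strict contradiction. That is fair. But the fault does not depend on a contradiction: the EAS rule, followed as written, loses these deaths.

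Fourth, restricting the EAS to response endpoints might be called a preference, or detail for the SAP. This does not stand. The protocol fixes both the set and its scope, and 9.7.5 makes any departure something the SAP must document. OS needs no scan, so an evaluability filter adds nothing to it and introduces selection on a post-treatment event.

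**Conclusion.** The concern holds and is minor. As written, the EAS can lose subjects who die before a postbaseline scan, and those deaths then disappear from sensitivity analyses of endpoints for which they are events.

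If no such death occurs, there is no effect from this source. One dropped death raises ORR by 0.6 points and the illustrative 12-month OS by 1.6 points; the assumed upper bound of three raises them by 2.0 and 5.2 points. The dropped deaths always push the response rates and later Kaplan–Meier estimates upward. The net direction for OS is not fixed, because living subjects without a scan are removed as well.

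These sizes rest on the assumed 0 to 3 dropped deaths, 6 responders, an exponential curve at the historical median, no early censoring, and the reading that subjects stopped for progression or toxicity are kept. DOR, the primary FAS analysis, the decision rule, and the stated type I error and power are unaffected.

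**What to change.** - **Section 9.7.1.2 and the synopsis:** state that subjects who died, or were discontinued because of progression or toxicity, before a postbaseline scan are included in the EAS and counted as nonresponders. This adds death, in line with 9.7.1.6.4 and 9.7.3, and settles whether the exception keeps or removes subjects.
- **Section 9.7.1.6.5:** limit the EAS sensitivity analyses to the response endpoints (ORR, CBR and DCR), and analyse PFS and OS in the FAS only.

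The cost is one clause in two places and one sentence, with no new data. The only downside is that EAS response rates may be slightly less favourable.
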